### **Specific Aim 3: Dyspnea on Exertion in Obese Children**

Introduction: DOE During Constant Load Submaximal Exercise. The *working hypothesis* is that childhood obesity will increase DOE and alter respiratory function during constant load submaximal cycling, but to a greater extent in obese children with respiratory symptoms misdiagnosed as asthma. The *rationale* behind the proposed research centers on the fact that exercising will force EELV to even lower levels in obese children creating the potential for significant breathing limitations. If low enough, obese children could experience tidal expiratory flow limitation, constrained expiratory tidal volume expansion, and decreased ventilatory capacity. It is unclear whether these respiratory effects or changes in body composition will be linked with DOE in obese children (i.e., increased RPB as it is in obese adults). Furthermore, we propose that obese children with respiratory symptoms misdiagnosed as asthma will have greater changes in EELV or differences in peripheral airways function making them more susceptible to the limitations of low lung volume breathing and/or increased ratings of dyspnea on exertion.

Methodology, experimental protocol, and measurements. The strategy will be to determine respiratory function, breathing mechanics, and DOE during 6 minutes of constant load submaximal exercise cycling at 30W (8-9 yr olds) or 40W (10-12 yr olds) and during 6 minutes of constant load cycling at 50% of peak  $\dot{V}O_2$ . We will measure HR, BP, SpO2%, PETCO2, gas

exchange ( $\dot{V}_E$ ,  $\dot{V}O_2$ ,  $\dot{V}CO_2$ , RER), RPB (Borg 0-10 scale), RPE (Borg 6-20 scale), and breathing mechanics (IC, EELV, EILV) including breathing pattern and tidal flow-volume loops continuously by standard methods used in prior studies. RPB and RPE will be measured every 2 min during the tests and the last values recorded will be used for analysis. We chose 30W and 40W to represent roughly ventilatory threshold where the exercise is not too easy or too difficult, and the participants can exercise continuously for 6–10 min as needed to get adequate assessment of RPB. We chose 50% to examine RPB and EELV at the same relative intensity. We selected cycling exercise because stationary cycling is affected less by body weight (and in a predictable manner) than treadmill exercise, we can impose smaller work rates more precisely, and we can compare the results in obese children to our previous findings in obese adults.

Expected results. We expect to have shown that in comparison with nonobese children otherwise healthy obese children have an increase in RPB and altered respiratory function (i.e., reduced EELV and increased expiratory flow limitation) during submaximal cycling, which may be correlated with other obesity-related changes in body composition and resting respiratory function. However, we expect that obese children with respiratory symptoms misdiagnosed as asthma will have greater changes in EELV or airway function making them more susceptible to low lung volume breathing and/or greater DOE. We also *expect* to have a better understanding of the importance of obesity-related alterations in respiratory function and breathing mechanics in obese children during exercise, and the differences (if any) between obese boys and girls.

Interpretation of results. We will interpret these results to suggest that obese children have significant obesity-related alterations in DOE and respiratory function during submaximal exercise, which predispose them to potentially clinical breathing limitations, especially in obese children misdiagnosed with asthma, all through a common mechanism of low lung volume breathing. This is important knowledge for the healthcare provider who sees obese children with symptoms on exertion. On the other hand, if obese children have RPB values similar to that in nonobese children during exercise, without association with other obesity-related changes, this would imply that increased chest wall fat and a lower EELV do not impair breathing during exercise as in obese adults, which would be important to document.

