### **Statistical Considerations**

Co-investigator [name] (UT Southwestern Division of Biostatistics) is the statistical co-investigator on this project and has assisted in the development of the statistical plan; she will also

Total n=96	Obese	Obese misdiagnosed with asthma	Non- obese
Boys	n=24	n=12	n=12
Girls	n=24	n=12	n=12

direct the data analysis on an on-going basis.

Statistical Plan. Our plan is to complete testing in nonobese and two obese groups, boys and girls separately but concurrently. Thus, sample size calculations are based upon within-gender comparisons per allocation in table at right. In Aims 1-3, comparisons will be made between nonobese, obese, and obese children misdiagnosed with asthma within the same gender with analysis of variance models (ANOVA). Pairwise group comparisons will be made using least squares means contrasts derived from the linear models. Data transformations or nonparametric tests will be utilized as needed to meet analysis assumptions. At baseline, ISSAC and ECRHS asthma screening questionnaire scores will be compared among groups with the Kruskal-Wallis test. Comparisons for Aim 4 will be made similarly, but with the addition of repeated measurements to assess the two obese groups and the nonobese children of the same gender at baseline and at 1 year of follow-up. Additional assessments of gender effects will be performed as part of a secondary analysis, but we are not powering the study to detect interaction by gender. Alpha is set at 0.05 for ANOVA and planned contrast power (PASS 11, NCSS, LLC, Kaysville, UT), described below . Data will be analyzed using SAS version 9.4 (SAS Institute, Inc., Cary, NC).

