Aim 1. Our primary variable is FRC measured while seated upright (Aim 1a) and when lying supine (Aim 1b). Based upon our preliminary data for seated FRC (%TLC) in nonobese boys (mean± SD, 42.4±2.5) and obese boys (36.5±6.2), it is calculated that a mean difference in FRC (%TLC) of 5.1 can be detected with statistical power of 81%, alpha=0.05, pooled SD of 5.0, comparing 24 obese to 12 nonobese children or to 12 obese children misdiagnosed with asthma. Our data also show that the differences may be larger for girls than boys, so power for a test between obese girls and obese girls misdiagnosed with asthma will be at least 80%. Similarly, for children lying supine, nonobese boys have an FRC (%TLC) of 34.4±8.8 vs. 23.1±3.4 obese, a more conservative difference of 6.0 %TLC is detectable with 80% power. In our formal protocol, we anticipate being able to make precise and reproducible measurements, and have confidence that we can meet our goals with the sample size proposed. Preliminary data demonstrate that these measures and effect sizes are feasible.

Aim 2. Our primary variable is peak  $\dot{V}O_2$ . From our preliminary peak  $\dot{V}O_2$  (ml/min/kg) for nonobese (41.9±4.9) and obese boys (26.3±3.9), it is calculated that our study will yield power of 80% to detect a clinically relevant mean difference of 4.7 ml/min/kg for obese versus nonobese children or obese children misdiagnosed with asthma, anticipating smaller differences than the 16 ml/min/kg mean difference observed from our data in obese versus nonobese. Effect size estimates for girls are anticipated to be similar.

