Aim 3. Our primary variable for Aim 3 is RPB during constant load exercise. Preliminary data from children in our lab show that RPB at constant load is very similar between nonobese and obese children of both genders (e.g., girls, 3.4±0.6 vs. 3.3±1.5), which would not be detectable with a reasonable sample size. This is in contrast with our previous studies of RPB in nonobese (2.1±1.3)  and obese women with DOE (4.7±1.2) , where only 6 subjects would have been necessary per group to detect significant differences. At this time our preliminary sample of children is small, and we anticipate that future experience could be more like that in the adults, but we need to carry out the designed studies at a feasible sample size (96 total including nonobese controls) to find out. These effects contrast with another important variable for Aim 3; the EELV during constant load exercise. Based upon EELV (%TLC) data from obese girls (28±3) during exercise, we would be able to detect differences of 3.2%TLC between the 3 groups at greater than 80% power (also note how low the EELV is in the obese children during exercise). We expect similar differences and power in studies with boys.

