**Aim 4.** Primary variables for Aim 4 are change in FRC at rest, peak  $\dot{V}O_2$ , RPB, and EELV during constant load exercise from before to after 1 year of follow-up. We are gaining experience with studies in children; current preliminary data from n=7 obese children yield similar mean differences and standard deviations as in adults. Therefore, based upon the change in EELV during constant load exercise in obese men before ( $35 \pm 5$ ) and after ( $39 \pm 3$ ) a loss of 13% of body fat, and the change in RPB during constant load exercise in obese women before ( $4.7 \pm 1.1$ ) and after ( $3.2 \pm 1.6$ ) weight loss, our sample will have sufficient power (.80,  $\alpha=0.05$ ) to detect meaningful paired differences (e.g., 1.5 in RPB) with weight loss and regular exercise. We will retest all children after ~1 yr. We expect less than 10% attrition and repeated data on nearly all children will be available for this Aim. Combining the two obese groups (with and with asthma misdiagnosis), the children will be divided into obese who lost weight, obese who gained weight, and control normal weight children and respiratory changes will be compared between groups with ANOVA as described for Aims 1-3. While these categorized weight changes have clinical appeal, weight change analyzed as a continuous variable may be more powerful and informative. Hence, change at 1 year minus baseline will also be evaluated with Spearman or Pearson correlations to quantify the association between 1-year weight change and the change for respiratory function, exercise tolerance, and DOE variables and, with the 36 obese participants analyzed (by gender), a correlation of 0.45 can be detected with 80% power.

To evaluate gender effects, baseline and follow-up measurements for FRC, peak  $\dot{V}O_2$ , RPB, and EELV will be analyzed in mixed-effects repeated measures models with the study participant included as a random effect. Interactions between gender, study group (obese, obese misdiagnosed with asthma, nonobese), and time can be assessed as fixed effects; weight change effect will be modeled as a covariate. PAQ-C score changes will also be assessed with repeated measures models.

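### Aim 3 would infer no adult-type breathing impairment from similar RPB, but the plan sets no criterion for similarity and its per-gender difference test misses a true 1-point excess 33–43% of the time at the pooled pilot SD

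*Combined protocol and SAP*

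**What the plan says.** Specific Aim 3 (Interpretation of results) covers two outcomes. The expected one is raised breathlessness in obese children. The other applies "if obese children have RPB values similar to that in nonobese children during exercise" and there is no association with other obesity-related changes. Chest wall fat and a reduced EELV would then be taken not to impair breathing on exercise in the way seen in obese adults.

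The Statistical Considerations section supplies the analysis:

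- Endpoint: "Our primary variable for Aim 3 is RPB during constant load exercise".
- Method: ANOVA within gender. "Pairwise group comparisons will be made using least squares means contrasts derived from the linear models".
- Error rate: "Alpha is set at 0.05 for ANOVA and planned contrast power".
- Size: "sample size calculations are based upon within-gender comparisons per allocation in table at right". The Aim 1 paragraph spells out the contrast as "comparing 24 obese to 12 nonobese children or to 12 obese children misdiagnosed with asthma".
- Power for RPB in children in Aim 3: none stated. The pilot means in girls (3.4±0.6 nonobese, 3.3±1.5 obese) are given as an example of a difference "which would not be detectable with a reasonable sample size". The pilot is described as small.
- The only RPB difference called meaningful is in Aim 4, where the sample is said to be able to "detect meaningful paired differences (e.g., 1.5 in RPB"). That is a within-child change with weight loss.

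No section gives a margin, a confidence-interval rule or an equivalence test for the word similar.

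**The concern.** A difference test can show that two groups differ. It cannot by itself show that they are alike. Where the text attaches a substantive negative conclusion to similarity and the plan offers only a difference test, the natural route to that conclusion is a p-value above 0.05. With 24 v 12 children per gender, such a p-value can occur often when obese children really are more breathless.

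The second condition does not guard against this. Absence of an association would also, in practice, be judged by not finding one.

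RPB is the primary variable of Aim 3, and the protocol presents the result as knowledge for providers who see obese children with symptoms on exertion. Imprecision reported as a lack of impairment could lead them to discount a real symptom.

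**Working it through.** **Inputs.** 24 obese v 12 nonobese per gender and alpha 0.05 (Statistical Considerations). Sidedness is not stated; two-sided is assumed because it reproduces the stated powers. Pilot RPB SDs in girls are 0.6 and 1.5 (Aim 3 paragraph); none is given for boys, so the same range is assumed.

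**Reproducing the plan's figures** (two-sample t, noncentral t power).
- Aim 1: difference 5.1, SD 5.0, 24 v 12 gives 80.0%; stated 81%.
- Aim 3 EELV: difference 3.2, SD 3 gives 83%; stated above 80%.
- Adult RPB: difference 4.7 − 2.1 = 2.6, pooled SD √[(1.3² + 1.2²)/2] = 1.25. Six per group gives 90% power and five gives 82%; the plan states 6 per group without a power.
- Aim 4 correlation: 0.45 with n = 36. atanh(0.45) × √33 = 2.784, and Φ(2.784 − 1.96) = 79.5%; stated 80%.

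The same method is therefore applied to RPB in children.

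**SD.** Equal weights: √[(1.5² + 0.6²)/2] = 1.14. Weighted to the planned sizes: √[(23 × 1.5² + 11 × 0.6²)/34] = 1.28. The obese girls' SD alone, 1.5, is taken as the upper case.

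**Precision and misses, one gender.** SE = SD × √(1/24 + 1/12) = SD × 0.354. The 95% CI half-width is 2.032 × SE (34 df). The chance of a miss comes from the noncentral t with noncentrality (true difference)/SE.

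| SD | SE | Half-width | Missed at 1.0 | Missed at 1.5 | Missed at 2.6 |
|---|---|---|---|---|---|
| 1.14 | 0.40 | 0.82 | 33% | 5% | <0.1% |
| 1.28 | 0.45 | 0.92 | 43% | 10% | <0.1% |
| 1.50 | 0.53 | 1.08 | 55% | 22% | 0.3% |

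The difference detectable with 80% power is 1.16, 1.31 and 1.53 points. Using the three-group error term (45 df) changes power at 1 point by less than one percentage point.

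**Genders combined** (48 v 24, SE = SD × 0.25). A 1-point excess is missed 7%, 13% and 25% of the time.

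**The no-association condition.** The plan gives a detectable correlation only for Aim 4. Assuming the same 36 obese children per gender, a true correlation of 0.30 gives atanh(0.30) × √33 = 1.778 and power Φ(1.778 − 1.96) = 43%. It would be missed about 57% of the time.

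**What a margin would do.** Suppose similarity is declared when the 90% CI lies wholly within ±1.5. Per gender, with no true difference, it is shown about 95%, 89% and 74% of the time (SD 1.14, 1.28, 1.5). With a true excess of 1.0 it is still declared 33%, 29% and 23% of the time. With a ±1.0 margin and no true difference, it is shown about 57%, 40% and 18% of the time per gender, and 93%, 85% and 68% with genders combined.

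**The case against.** Several stronger readings are tempting, and the documents do not support them.

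- **That the plan equates similar with non-significant.** It does not say so. The Aim 3 text mentions no test, and the statistical section uses the word for pilot means only 0.1 apart. An observed gap of 0.1 would have an upper 95% limit of 0.1 + 0.82 to 0.1 + 1.08, about 0.9–1.2 points. The link to non-significance is an inference, resting on the difference test being the only primary tool provided.
- **That the plan admits it lacks precision.** The remark "which would not be detectable with a reasonable sample size" concerns a near-zero pilot difference, with obese girls slightly lower. It says nothing about power for 1 point, and the same paragraph leaves the question open.
- **That a null result would be read as no impairment of any kind.** The sentence is qualified by comparison with obese adults. If only an adult-size effect (2.6 points) is being denied, the per-gender test misses it at most 0.3% of the time and a null result supports the claim.
- **That RPB is compared only within gender.** Mixed models including RPB, gender, study group and time are also planned. They are there to evaluate gender effects, which the plan makes a secondary analysis.

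Other points in the plan's favour also stand. If both genders had to be null, and independently so, the chance at a true 1 point falls to 0.33² to 0.43², about 11–18%. With the pilot's unequal SDs, simulated power at 1 point is about 79% by Welch's test, against 60% by the pooled-variance test. The sentence is a conditional remark in a narrative section and triggers no action. These points reduce the size of the problem, but none defines similarity.

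**Conclusion.** The concern holds in a limited form. Similarity carries a negative conclusion without a criterion, and the primary tool that would probably be used to judge it misses a true 1-point excess 33–43% of the time per gender at the pooled pilot SD, and 55% at SD 1.5. At 1.5 points the misses are 5–10% (22% at SD 1.5). The plan can therefore support exclusion of an adult-size effect, but a non-significant result alone cannot support a claim that obese children have no excess breathlessness of about 1 point.

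This rests on two-sided testing, on reading similar as not significant, and on SDs from a small pilot in girls. If the SD were about 1.0, power at 1 point would be about 79% and the problem correspondingly smaller.

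**What to change.** Amend the Aim 3 interpretation as follows.

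1. Conclude absence of impairment only if the upper limit of the 90% CI for obese minus nonobese RPB lies below a between-group margin fixed and justified before analysis. Give the interval for each gender and, ideally, for genders combined (48 v 24).
2. Otherwise report the difference with its CI as inconclusive, or limit the conclusion to excluding an adult-size effect of 2.6 points.
3. Report any correlations with their CIs, and do not treat a non-significant one as no association.

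The 1.5 points in Aim 4 is a paired change and can serve only as an outer bound for the margin. A 1.5 margin does not cure misses at 1 point, because similarity within 1.5 would still be declared 23–33% of the time per gender when the true excess is 1.0. If 1 point matters, the margin must be tighter, and the combined-gender comparison becomes the practical one.

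The cost is wording and one added interval, with no new data or participants. The downside is that some null results will have to be called inconclusive.

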#### **Specific Aim 4: Effects of Weight Loss and Regular Exercise and Weight Gain in Obese Children**

Introduction. The *working hypothesis* is that weight loss (or an equivalent reduction in BMI percentile) and regular exercise will improve respiratory function, exercise tolerance, and DOE in obese children, including obese children misdiagnosed with asthma, while continued weight gain (or increase in BMI percentile) will worsen respiratory function, exercise tolerance, and DOE in obese children, including obese children misdiagnosed with asthma, as compared with normal weight children after 1 yr. The *rationale* behind the proposed research centers on the fact that FRC at rest, EELV during exercise, and peak  $\dot{V}O_2$  in ml/min/kg will be increased in obese children after weight loss and regular exercise but decreased by continued weight gain. The cumulative effect of the weight loss program would thereby reduce the potential for breathing limitations at rest and/or during exercise, increase exercise tolerance, and potentially reduce DOE in obese boys and girls, including those misdiagnosed with asthma, but weight gain would have the reverse effects.

Methodology, experimental protocol and measurements. The strategy will be to repeat the measurements detailed in Aims 1-3 after 1 yr: 1) in 12 obese boys and 12 obese girls after weight loss (or an equivalent reduction in BMI percentile) and regular exercise, 2) in 12 obese boys and 12 obese girls after weight gain (or an increase in BMI percentile), 3) in 12 obese boys and 12 obese girls misdiagnosed with asthma regardless of weight changes or exercise participation, and 4) in 12 normal weight boys and 12 normal weight girls. We will test at 1 yr because parents **prefer** to have testing done during summer vacation months only.

*Weight Loss and Regular Exercise* will be prescribed by attending physicians at the **COACH**

Program at Children's Medical Center (Director [name] is co-investigator, see Facilities & Letter of Support). However, all obese children will receive standard of care information regarding weight loss and physical activity if they elect not to enter **COACH**. At **COACH**, the participant and parents will meet with a registered dietician who will perform a diet assessment and offer a meal plan for an initial weight reduction of  $\approx 10\%$  of body weight or an equivalent reduction in BMI percentile (e.g., growth of 2.5 cm would lower BMI percentile by  $\approx 1$  based on CDC growth charts). This change in weight or in BMI should yield significant changes in respiratory function based upon our prior adult data and our preliminary data. Participants will then meet with nurses, and physical therapists in the **COACH** behavior modification class where they will be encouraged to participate in 60-min of moderate intensity physical activity per day. Finally, they will meet with the physician who will discuss clinical test results (i.e., blood work to eliminate diabetes, impaired glucose tolerance, impaired fasting glucose, dyslipidemia, liver enzyme elevation, vitamin D deficiency or insufficiency), and review the overall diet and physical activity plan. We will schedule retesting after 1 yr.

To increase the likelihood of success of the weight loss and regular exercise, we will establish a biweekly phone-contact schedule with **COACH** participants. We will not interfere with the dietary and medical recommendations set forth by **COACH** faculty, but we will act as liaisons and supporters. Specifically, we will be available to answer any questions that might arise regarding diet and physical activity recommendations. The results of the constant load and incremental exercise tests will be used to provide a guide of appropriate physical activity intensities (e.g., based on VTh, peak HR, peak  $\dot{V}O_2$ , & ACSM guidelines). We will invite the participants and parents to meet with us and we can demonstrate these physical activity intensities on multiple exercise devices depending on the preferences of the patient (e.g., stationary cycle, treadmill, etc.). Our goal will be to encourage regular exercise (i.e., increase energy expenditure), not to design an exercise training program for improvement of cardiorespiratory fitness. Consequently, activity levels will not be quantified (i.e., controlled & supervised exercise intensity, duration, & frequency). We will note biweekly whether the children have been active as recommended and we will administer the Physical Activity Questionnaire-Children (PAQ-C) before and after 1 yr.

All children who completed Aims 1-3 will be tested at 1 yr whether they lose weight or gain weight. The retesting in nonobese children will be used as control data to document the effect of age and growth on respiratory function, exercise tolerance, and DOE.

Expected results. We expect that a program of weight loss (or an equivalent reduction in BMI percentile) and regular exercise will increase FRC at rest and EELV during exercise while weight gain will decrease these. The change in FRC and EELV may be correlated with changes in body composition (if any). These improvements in respiratory function and breathing mechanics may also be associated with decreased DOE as well, while weight gain would have the reverse effects. Exercise tolerance will be increased in ml/min/kg but we expect no change in cardiorespiratory fitness (i.e., Peak  $\dot{V}O_2$  as percent predicted based on ideal body weight), which may actually be slightly decreased, including those misdiagnosed with asthma. With weight gain, exercise tolerance will be decreased but cardiorespiratory fitness would be unchanged as well. We also *expect* to have a better understanding of the importance of weight loss and regular exercise and weight gain on respiratory function and breathing mechanics in obese children, and the differences (if any) between obese boys and girls.

Interpretation of results. We will interpret these results to suggest that weight loss (or an equivalent reduction in BMI percentile) and regular exercise will have a significant improvement on respiratory function, exercise tolerance, and DOE, while weight gain will worsen respiratory function, exercise tolerance, and DOE in obese children all through a common mechanism of increasing or decreasing EELV. Weight loss may also reduce potential clinical breathing limitations at rest and during exercise (e.g., expiratory flow limitation) but weight gain would increase limitations. This would be important knowledge for healthcare providers who may not appreciate the obesity-related respiratory effects in obese children, and who may assume that

symptoms such as breathlessness are just due to cardiovascular deconditioning and/or asthma. In contrast, if obese children have a simple increase in EELV with weight loss without association with other changes in respiratory function, exercise tolerance, and DOE, this would be clinically important to document as well. The same would be true if there were no negative effects of weight gain. These findings, while very unlikely, would suggest that chest wall fat and changes in respiratory function are not the lone sources of obesity-related breathing limitations and bring to question what effects weight loss and regular exercise, and weight gain might have on respiratory function, exercise tolerance, and DOE.

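### Aim 4 plans to credit improvement to weight loss and regular exercise, but its analysis groups children by weight change alone and can show only an association with weight change

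*Combined protocol and SAP*

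**What the plan says.** **Design and interpretation (Specific Aim 4).** One of the four retested groups is described as "in 12 obese boys and 12 obese girls after weight loss (or an equivalent reduction in BMI percentile) and regular exercise". A second group consists of obese children who gained weight. The third, the children misdiagnosed with asthma, is retested regardless of weight change or exercise participation. The fourth is the normal weight children. The interpretation paragraph takes the results to suggest that weight loss (or an equivalent fall in BMI percentile) and "regular exercise will have a significant improvement on respiratory function, exercise tolerance, and DOE", through a common mechanism of change in EELV.

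**Programme entry (Specific Aim 4).** Weight loss and exercise are prescribed at COACH, but "all obese children will receive standard of care information regarding weight loss and physical activity if they elect not to enter" the programme. Families therefore choose.

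**Activity data (Specific Aim 4).** The plan states that "activity levels will not be quantified", meaning that exercise intensity, duration and frequency are not controlled or supervised. Some activity data are still collected: a biweekly note of whether children have been active as recommended, and "we will administer the Physical Activity Questionnaire-Children (PAQ-C) before and after 1 yr".

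**Analysis (Statistical Considerations, Aim 4).** The two obese groups are combined, and "the children will be divided into obese who lost weight, obese who gained weight, and control normal weight children" for ANOVA. Weight change is also correlated with outcome change (Spearman or Pearson, unadjusted), with 36 obese participants per gender and 80% power for a correlation of 0.45. The mixed models for FRC, peak VO2, RPB and EELV contain gender, study group and time, with weight change as the one added covariate. For activity, the plan says only that "PAQ-C score changes will also be assessed with repeated measures models".

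**The concern.** The conclusion names two exposures, and the outcome analyses contain one of them. A child who became active but gained weight is counted with the gainers. A child who lost weight without exercising is counted with those whose improvement will be credited partly to exercise. No planned model for FRC, peak VO2, RPB or EELV contains activity or COACH participation.

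Peak VO2 and DOE could respond to a change in activity even if weight does not change. If children who become more active also tend to lose weight, part of a difference between losers and gainers may come from activity. The Aim 4 interpretation also says the findings would inform providers who put breathlessness down to deconditioning or asthma. An analysis without activity cannot separate that explanation from a weight and EELV mechanism.

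**Working it through.** **1. Can the weight group stand in for exercise or for the programme?** Three statements in the plan say no.

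- Recruitment of subjects reports that half of the obese children in the pilot lost weight and half gained, with no study contact in between. Losing weight therefore does not imply taking part in the supported programme.
- The children misdiagnosed with asthma are retested regardless of exercise participation and are then pooled into the lost and gained groups. They number 24 of 72 obese children, 24/72 = one third.
- COACH entry is elective, the biweekly telephone contact is scheduled for COACH participants, and COACH participation is not an analysis factor.

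**2. The plan's own power figure.** Inputs from Statistical Considerations are r = 0.45, n = 36 and alpha = 0.05 (taken as two-sided). With k adjusting covariates, Fisher's z gives

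power = Phi(atanh(r) × sqrt(n − 3 − k) − 1.96).

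For k = 0: atanh(0.45) = 0.485, 0.485 × sqrt(33) = 2.78, and Phi(2.78 − 1.96) = 79.5%. A bias-corrected version gives 80.5% and simulation 80.6%. The stated 80% is reproduced.

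**3. What confounding by activity could do.** The documents give no correlations involving activity, so these are assumptions. Suppose weight change has no direct effect, activity change correlates p with weight change and q with outcome change, and p = q. The weight–outcome correlation is then p × q.

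| Assumed p = q | Induced r | Unadjusted test at n = 36 rejects |
|---|---|---|
| 0.3 | 0.09 | about 8% |
| 0.4 | 0.16 | about 15% |
| 0.5 | 0.25 | about 32% |
| 0.7 | 0.49 | about 88% |

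The 0.4 row uses Fisher's z and the others use simulation. The nominal rate is 5%. In simulations at 0.3, 0.5 and 0.7, adjusting for activity measured without error brought the rejection rate back to about 5%.

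**4. What adjustment costs.** At a fixed partial r of 0.45 and n = 36:

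- one covariate (PAQ-C change): Phi(0.485 × sqrt(32) − 1.96) = 78.3%, about 1 point lost;
- three covariates (adding COACH participation and baseline BMI): Phi(0.485 × sqrt(30) − 1.96) = 75.6%, about 4 points lost.

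Shared variance can cost much more. If the marginal correlation is 0.45, the partial correlation is (0.45 − pq)/sqrt((1 − p²)(1 − q²)).

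- p = q = 0.3: 0.36/0.91 = 0.40, power about 67%.
- p = q = 0.5: 0.20/0.75 = 0.27, power about 35%.

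These two power figures use the bias-corrected version with one covariate.

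**The case against.** The strongest reply is the scope limit in Overall Strategy. The study disclaims the effectiveness of the intervention, the dose response of diet and exercise, and the rate of weight loss, and studies only the response to weight loss with regular exercise or to continued weight gain. On that reading the exposure is a bundle and the plan never set out to separate its parts. This stands in part: the plan need not estimate an exercise effect. It does not rescue the conclusion, because the groups analysed are defined by weight alone and are not the bundle. Nothing in the plan limits the Aim 4 interpretation to association.

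Three other points have some force. The interpretation is phrased as what results suggest, and the plan gives alternative readings if the expected associations do not appear. Peak VO2 as percent predicted for ideal body weight, which the plan expects not to rise, is a partial check on a fitness effect. The nonobese children control for age and growth. None of these addresses differences in activity between obese losers and gainers.

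A reader might infer that children select themselves into the weight groups. The documents do not support that: families choose whether to enter COACH, whereas losing or gaining is a measured 1-year result. A reader might also infer from "activity levels will not be quantified" that activity goes unrecorded. It does not, since the PAQ-C and a biweekly note are planned; what is missing is their use in the outcome models.

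**Conclusion.** The concern holds as a mismatch between analysis and conclusion. Comparing "obese who lost weight, obese who gained weight" and the controls, together with unadjusted correlations, describes how outcomes vary with weight change, and those analyses are valid for that purpose. They do not support an effect of exercise or a causal effect of weight loss. The problem is sharpest for peak VO2 and DOE and less evident for FRC and EELV, where no comparable route from activity has been argued.

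The size cannot be derived from the documents. The range of about 8% to 88% rests on assumed equal correlations from 0.3 to 0.7 and no direct weight effect. It shows what is possible, not what is expected. It would go too far to say that activity explains any weight association that is found, because the plan gives no data on how activity relates to weight or outcome change.

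**What to change.** Keep the planned Aim 4 analyses. Pre-specify one supportive model for each Aim 4 primary variable (change in FRC, peak VO2, RPB and EELV) with weight (BMI) change and PAQ-C change together. Add COACH participation (yes/no) and baseline BMI as further covariates where n allows. Report the result beside the unadjusted one.

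Reword the Aim 4 interpretation as an association with weight change. Describe any relation with PAQ-C change as an association too, since it would come from the same non-randomised data.

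The PAQ-C and BMI data are already planned, and COACH participation is known to the team, so the work is one more model per variable plus wording. The costs are:

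- about 1 point of power for one covariate and about 4 for three at a fixed partial r of 0.45, and far more if activity and weight change share variance;
- residual confounding, because the PAQ-C is a questionnaire;
- possible over-adjustment, because activity may lie on the causal path.

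For these reasons the adjusted model should supplement the planned analysis and not replace it.
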